16.2.2 Other secondary endpoint analyses

The following efficacy endpoint analyses will be performed for the primary analysis and presented on the mITT Analysis Set:

- ACR20 response at each visit
- ACR50/ACR70 response at each visit
- Change and percent change in hsCRP from Baseline to Week 12
- CFB in DAS28-hsCRP score at Week 4 and Week 12
- Percentage of subjects with DAS28-hsCRP < 3.2 (well-controlled disease) at Week 12
- Percentage of subjects with DAS28-hsCRP < 2.6 at Week 12
- CFB in ESR, anti-CCP, RF (at Week 4 and Week 12)
- CFB to Week 12 in subject's self-assessments including:
 - Global assessment of disease activity (VAS)
 - Self-assessment of pain (VAS)
 - Self-assessment of disability (HAQ-DI)
- CFB to Week 12 in Physician's Global Assessment of Disease Activity (VAS).

The Week 12 hsCRP CFB will be analyzed in the same way as the Week 4 hsCRP CFB, ie descriptive statistics, ANCOVA model and sensitivity analysis using Hodges-Lehmann difference median estimate and 80% CI. This analysis will also be applied to DAS28-hsCRP score CFB at Week 4 and Week 12. The DAS28-hsCRP will be derived using the formula presented in [Appendix 2](#).

ACR50 and ACR70 are defined in the same way as the ACR20 using at least 50% and 70% improvement, respectively. The ACR50 and ACR70 proportions will be analyzed in the same way as the Week 12 ACR20 proportions.

This analysis will also be applied to Week 12 "DAS28-hsCRP < 3.2" proportion and Week 12 "DAS28-hsCRP < 2.6" proportion, but without the sensitivity analysis.

Proportions of ACR20/50/70, "DAS28-hsCRP < 3.2" and "DAS28-hsCRP < 2.6" will also be presented by treatment group and time point as observed, ie without any imputation.

Descriptive statistics

Descriptive statistics will be tabulated by treatment group and time point for the following continuous variables, both absolute value and CFB. The summary statistics will be provided as observed without imputation of missing data.

- DAS28-hsCRP score
- hsCRP (CFB and percent CFB)
- ESR
- anti-CCP
- RF

- TJC68 (CFB and percent CFB)
- SJC66 (CFB and percent CFB)
- subject's global assessment of disease activity (CFB and percent CFB)
- subject's assessment of pain (CFB and percent CFB)
- subject's self-assessment of disability (HAQ-DI) (CFB and percent CFB)
- Physician's Global Assessment of Disease Activity (CFB and percent CFB)

Each of the following parameters will be also displayed by categories. The number and percentage of subjects at Week 4 and Week 12 will be computed and a shift table from baseline to Week 4 and Week 12 respectively will be provided. For all shift tables, data will be summarized as observed, ie no imputation on missing data. The following parameters will be presented into categories:

- hsCRP (mg/L) by category (normal/high based on central normal laboratory ranges)
- DAS28-hsCRP, derived using the formula presented in [Appendix 2](#), summarized by disease activity category (< 2.6 [remission], ≥ 2.6 to ≤ 3.2 [low], > 3.2 to ≤ 5.1 [moderate] and > 5.1 [high]).
- ESR (mm/Hr) by category (low/normal/high based on local normal ranges collected in eCRF)
- Acute-phase reactant (at least one test result is needed for the classification): normal hsCRP and normal ESR, abnormal hsCRP or abnormal ESR. Abnormal refers to either below or above the normal range classification.
- RF (expressed in kU/L) classified as negative (\leq ULN) and positive ($>$ ULN)
- anti-CCP classified as negative (\leq ULN) and positive ($>$ ULN)
- Serology (at least one test result is needed for the classification): negative RF and negative anti-CCP (\leq ULN), low-positive RF or low-positive anti-CCP ($>$ ULN, $\leq 3*ULN$), high-positive RF or high positive anti-CCP ($>$ $3*ULN$)

Box plots will be performed for each ACR component and DAS28 at each timepoint. Both treatment groups will be presented in the same graph. One plot will present the CFB and another plot for the percent CFB). Data will be displayed as observed, ie without any imputation.

Line plots will be generated for ACR response at each visit over time for both primary and final analysis as follows:

- For the primary analysis, both treatment groups will be displayed.
- For the final analysis, only the M2951 50 mg BID/ M2951 50 mg BID subjects will be presented.
- Data will be presented using the LOCF-NR method, as for the primary endpoint.

16.3 Other Endpoint Analyses

16.3.1 Open-label Extension Endpoint Analyses

Descriptive statistics will be provided for data observed in the OLE period, and no imputation of missing data will be performed:

- Continuous endpoints: summary statistics will be provided for each group.
- Categorical endpoints: number and frequency of subjects in each category will be reported for each group.

The following efficacy endpoint analyses will be performed for the final analysis and presented on the OLE mITT Analysis Set:

- ACR20/ACR50/ACR70 response at Month 6
- Absolute value, CFB and percent CFB in hsCRP at Month 6
- Absolute value, CFB in DAS28-hsCRP score at Month 6
- Percentage of subjects with DAS28-hsCRP < 3.2 (well-controlled disease) at Month 6
- Percentage of subjects with DAS28-hsCRP < 2.6 at Month 6
- Absolute value, CFB in ESR, anti-CCP, RF at Month 6
- Absolute value, CFB and percent CFB in TJC68, SJC66 at Month 6
- Absolute value, CFB and percent CFB to Month 6 in subject's self-assessments including:
 - Global assessment of disease activity (VAS)
 - Self-assessment of pain (VAS)
 - Self-assessment of disability (HAQ-DI)
- Absolute value, CFB and percent CFB to Month 6 in Physician's Global Assessment of Disease Activity (VAS).

Each of the following parameters will be also displayed into categories. The number and percentage of subjects at Month 6 will be computed and a shift table from baseline to Month 6 will be provided. For all shift tables, data will be summarized as observed, ie no imputation on missing data. The following parameters will be presented into categories:

- hsCRP (mg/L) by category (normal/high based on central normal laboratory ranges)
- DAS28-hsCRP, derived using formula presented in [Appendix 2](#), summarized by disease activity category (< 2.6 [remission], ≥ 2.6 to ≤ 3.2 [low], > 3.2 to ≤ 5.1 [moderate] and > 5.1 [high]).
- ESR (mm/Hr) by category (low/normal/high based on local normal ranges collected in eCRF)

- Acute-phase reactant (at least one test result is needed for the classification): normal hsCRP and normal ESR, abnormal hsCRP or abnormal ESR. Abnormal refers to either low or high normal range classification.
- RF (expressed in kU/L) classified as negative (\leq ULN) and positive ($>$ ULN)
- anti-CCP classified as negative (\leq ULN) and positive ($>$ ULN)
- Serology (at least one test result is needed for the classification): negative RF and negative anti-CCP (\leq ULN), low-positive RF or low-positive anti-CCP ($>$ ULN, $\leq 3*$ ULN), high-positive RF or high positive anti-CCP ($>$ $3*$ ULN)

16.3.2 Pharmacokinetic Endpoint Analyses

Analysis of the PK of M2951 and the associated figures will be the responsibility of the clinical pharmacokineticist at PPD [REDACTED]. The PK summaries and data listings as well as the statistical analysis of the PK parameters will be the responsibility of the study biostatistician at PPD [REDACTED].

For the PK analysis, predose sample M2951 concentrations that are BLQ will be assigned a numerical value of zero. On Day 1, any missing predose value will also be assigned a numerical value of zero for the calculation of AUC. Any anomalous concentration values observed at predose will be identified in the CSR. All postdose BLQ concentrations will be set to 'zero' in all cases. Graphical displays of mean (\pm SD for linear profiles only) plasma concentration-time profiles will be presented on linear and semi-logarithmic scales by dose level with Day 1 and Day 29 data on the same plot.

Non-compartmental computation of M2951 PK parameters will be performed. Pharmacokinetic parameters will be evaluated and listed for all patients who provide sufficient concentration-time data.

Individual PK parameters will be calculated using actual elapsed time from dose with a maximum of 14 significant digits in the time data (or using scheduled time if actual time is not available). The predose sample will be considered as if it had been taken simultaneously with the administration of IMP.

For each subject in the PK analysis set the following PK parameters will be calculated for M2951 on Day 1 and Day 29 following the morning dose on Days 1 and 29:

AUC _{0-6h}	Area under the plasma concentration-time curve from time zero to 6 hours after morning dosing, calculated according to the mixed log linear trapezoidal rule (ie, linear up/log down). Units: h*ng/mL.
C _{max}	Maximum plasma concentration observed after morning dose, obtained directly from the observed concentration versus time data. Units: ng/mL.

t_{\max}	Time to reach maximum plasma concentration, obtained directly from the observed concentration versus time data. Units: h.
C_{trough}	the concentration observed immediately before next dosing (Day 29 only). Units: ng/mL.
$R_{\text{acc(AUC0-6h)}}$	Accumulation ratio for AUC, calculated as ratio of AUC's: $AUC_{0-6h, \text{Day29}}/AUC_{0-6h, \text{Day1}}$.
$R_{\text{acc}(C_{\max})}$	Accumulation ratio for C_{\max} , calculated as ratio of C_{\max} 's: $C_{\max, \text{Day29}}/C_{\max, \text{Day1}}$.

16.3.3 Pharmacodynamic Endpoint Analyses

Absolute B cell numbers and subtypes (mature-naïve, non-switched, immature/transitional, memory), are assessed at screening and Days 1, 29, and 85 (end of treatment), prior to the morning dose in the 12-week treatment period. In addition absolute B cell numbers and subtypes will be assessed in the optional OLE period at Month 3, Month 6, and at the End of Trial Visit. Immunoglobulin levels (IgA, IgM, and IgG and subclasses) will be assessed at screening, Day 57 and Day 85 (end of treatment) in the treatment period, and at Month 3 and Month 6 visits in the OLE period.

Absolute B cell, B cell subtypes, and immunoglobulin levels (observed, change from baseline, and percent change from baseline values) will be summarized using the relevant PD analysis set. Descriptive statistics for these variables (mean, SD, CV%, median, minimum/maximum, Q1 and Q3 percentile, and interquartile range) will be presented.

The mean (SD) absolute value for each treatment group will be plotted versus time point for B cell, B cell subsets (mature-naïve, non-switched, immature/transitional, memory), and IgM, IgA, IgG immunoglobulin levels and IgG subclasses IgG1-IgG4. Similar plots of the mean (SD) percent change from baseline for each treatment group versus time point will be generated for B cell and B cell subtypes (mature-naïve, non-switched, immature/transitional, memory), NK cell, T cell, T cell subtypes (CD4 and CD8) and IgM, IgA, and IgG (and IgG subclasses) immunoglobulin levels.

16.3.4 Exploratory Endpoints

CCI
[Redacted text block containing multiple lines of blacked-out content]

CCI
[Redacted]

CCI
[Redacted]

[Redacted]

[Redacted]

[Redacted]

17 Safety Evaluation

The subsections in this section include specifications for summarizing safety endpoints that are common across clinical trials such as AEs, laboratory tests and vital signs.

For all safety endpoints, data selection for primary and final analyses will be handled as indicated in the Table 15:

Table 15 : Data handling for safety analysis

Analysis	Population	Period covered	Treatment groups	Data to be analyzed
Primary analysis	Safety Analysis Set	12-Week treatment period until start of OLE or discontinuation of treatment prior to OLE, whichever is applicable	Placebo or M2951 50 mg BID	All Data collected during the 12-Week treatment period up to start of OLE if applicable
Final analysis	OLE Safety Analysis set	OLE period only	Placebo/M2951 50 mg BID only	Data from OLE period only, or posterior to OLE (Safety follow-up / End of Study)
		Both 12-Week treatment period and OLE period	M2951 50 mg BID/M2951 50 mg BID only	Data from both periods (12-Week treatment and OLE period), ie all data collected throughout the study

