5.1 Overall Trial Design and Plan

This is a Phase IIa randomized, double-blind, placebo-controlled trial in approximately 64 subjects 18 to 75 years of age with RA on stable MTX background therapy.

Total duration of subject participation is approximately between 5 months (20 weeks) to 11 months (46 weeks), which includes:

- Screening: 28 days (4 weeks)
- Treatment: 84 days (12 weeks)
- Optional 6-month open-label extension period (26 weeks)
- Safety Follow-Up: 28 days (4 weeks)

After completing the 12-week treatment period, subjects will be offered the opportunity to participate in an optional 6-month open-label extension period where all subjects will receive M2951. For subjects who choose to participate in the optional extension period, the duration of participation will last a total of approximately 11 months.

Subjects who continue to receive M2951 during the extension period will also be required to undergo the Safety Follow-up Visit scheduled for approximately 28 days after the last treatment visit.

Screening will occur over Day -28 to -1 (Visit 1), during which time all Screening assessments must be completed and reviewed.

On Day 1 (Visit 2), after confirmation of eligibility, assessment of RA disease activity and vital signs, and obtaining of required blood and urine samples, subjects will be randomly assigned 1:1 to receive M2951 or placebo in combinations with MTX. **CCI**

Blood and urine samples will be obtained for safety (hematology, biochemistry, coagulation, and urinalysis), markers of disease activity (hsCRP, ESR, anti-CCP, and RF), PK (M2951 concentration), and PD (immunoglobulin levels, **CCI**, and B cell numbers) following the schedule detailed in the Schedule of Assessments ([Table 1](#)).

CCI

Subjects will self-administer the IMP at a set time each day (\pm 2 hours). Subjects must take their daily dose more than 1 hour prior to a meal or snack or more than 2 hours after a meal or snack. Clear fluids are allowed at any time. On trial visit days, the IMP will be administered during the trial visit after the trial visit procedures (other than PK/PD sampling) are completed.

[figure not shown]
Subjects will have trial visits weekly for the first 3 weeks of treatment; bi-weekly up until 8 weeks of treatment; a final On-Treatment Visit on Day 85 (12 weeks), and then return for 1 Follow-Up Visit approximately 28 days (4 weeks) after the last dose of IMP.

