8.5.5 Analysis of Safety and Other Endpoints

The analysis set for the safety assessments will be the Safety Analysis Set for the primary analysis and the OLE Safety Analysis Set for final analysis.

All safety endpoints will be summarized by treatment group unless otherwise specified. Analyses including both for the first 12-week treatment period and open-label extension period data will be summarized according to treatment groups 'M2951+MTX' and 'Placebo+MTX/M2951'.

Adverse events will be coded according to the Medical Dictionary for Regulatory Activities (MedDRA). The severity of AEs will be graded using NCI-CTCAE v4.03 toxicity grades (20). Adverse events with missing classification concerning IMP relationship will be considered related to the IMP.

The number and percentage of subjects experiencing 1 or more TEAEs will be summarized according to the MedDRA system organ classes and preferred terms by treatment group, relationship to IMP, and severity. Exposure-adjusted incidence rates of TEAEs will also be reported according to the MedDRA system organ class and preferred term.

Clinical laboratory parameters being monitored for safety will be summarized using descriptive statistics, by postdose shifts relative to Baseline for relevant parameters using relevant cutoffs as detailed in the SAP, box and whisker plots as relevant, and data listings of clinically significant abnormalities/outliers. Subject listings and summary statistics at each assessment time will be presented using the International System of Units (SI units).

Observed values and change from Baseline in vital signs and ECG data will be summarized for each treatment group using descriptive statistics. Clinically noteworthy physical examination, ECG, and CXR findings for individual subjects will be listed and summarized as appropriate.

At the end of the study, for final analysis, safety endpoints will be reported both for the first 12-week treatment period and for entire study, by treatment group, based on OLE Safety Analysis Set.

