17.1 Adverse Events

All analyses described in Section 17.1 will be based on treatment-emergent adverse events (TEAEs) if not otherwise specified.

TEAEs will be defined according to Table 16.

Table 16: Definition of TEAE

Primary analysis
	
TEAEs will be defined as AEs starting on or after first treatment administration of any IMP (placebo or M2951) until first dose of M2951 during OLE (or until the end of study if the patient declined to participate in OLE period).
 
Only AEs from 12-Week treatment period will be considered.

Final analysis
	
 • For subjects who switch from placebo to M2951 50 mg BID, TEAEs will be defined as AEs starting on or after first treatment administration of M2951 50 mg BID during OLE until the end of study. Only AEs from OLE period will be considered. • For patients who continue with M2951 50 mg BID during OLE, TEAEs will be defined as AEs starting on or after first treatment administration of M2951 during 12-Week double blind treatment period. AEs from both periods (12-Week treatment and OLE) will be considered.

Incomplete AE-related dates will be handled as follows:

- In case the onset date is missing completely or missing partially but the onset month and year, or the onset year are equal to the start of IMP then the onset date will be replaced by the minimum of start of IMP and AE resolution date.
- In all other cases the missing onset day or missing onset month will be replaced by 1.
- Incomplete stop dates will be replaced by the last day of the month (if day is missing only), if not resulting in a date later than the date of subject's death. In the latter case, the date of death will be used to impute the incomplete stop date.
- Further information collected after the cut-off for an analysis (such as a fatal outcome) may be extracted from the Safety data base and presented separately in the CSR.

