17.3 Clinical Laboratory Evaluation

The following laboratory parameters will be measured during the trial as part of the safety evaluation:

- Hematology
- Biochemistry
- Urinalysis
- Coagulation

The clinical laboratory safety tests to be measured in this trial are provided in the protocol (refer to Section 7.4.3 Table 4 of the Clinical Trial Protocol [CTP]).

Continuous protocol-specified clinical laboratory findings (hematology, biochemistry, urinalysis, coagulation) will be summarized by treatment using descriptive statistics (see [Section 11](#)). The statistics will be presented for baseline, each time point during the study, and CFB to each time point, when applicable.

Laboratory results will be classified according to NCI-CTCAE Version 4.03 as provided by the central laboratory. In case a laboratory parameter has bi-directional toxicities (eg Potassium) both directions will be presented for the given parameter (ie Potassium Low and Potassium High). On-treatment values are results of assessments done from the first IMP administration on Day 1. Laboratory results containing a modifier such as “<” or “>=” will be handled case by case for summary statistics and will be reported as collected in the database in subject data listings.

A shift table of baseline versus post-baseline based on the worst NCI-CTCAE grade will be presented by treatment group for hematology and biochemistry.

Additional laboratory results that are neither classified in protocol nor part of NCI-CTCAE will be presented according to the categories based on normal ranges: below normal limits (Low), within normal limits (Normal), and above normal limits (High). Classification into categories will be presented in subject data listings only.

Boxplots of the laboratory values (by treatment arm) by time point will be provided for:

- Hemoglobin
- Absolute reticulocyte count
- White blood cell count
- Absolute neutrophil count
- Absolute lymphocyte count
- Platelet count
- Alanine aminotransferase (ALT)
- Aspartate aminotransferase (AST)
- Gamma-glutamyl transferase (GGT)
- Total bilirubin
- Amylase
- Lipase
- Creatinine
- Blood urea nitrogen (BUN)

Boxplots for laboratory parameters where toxicity grades are defined based on the ratio of the parameter values and the ULN will not be displayed using the unit of measurement but instead using the ratio of the measured value over ULN. This comprises the following parameters:

- ALT
- AST
- GGT
- Total bilirubin
- Creatinine
- Amylase

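### The final safety tables set about 30 weeks of observation for switchers beside about 42 for continuers, so crude AE percentages and worst laboratory grades for events compatible with extension entry can differ through window length alone

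*SAP*

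**What the plan says.** Protocol Section 8.5.5 sets this rule for the last report: "safety endpoints will be reported both for the first 12-week treatment period and for entire study, by treatment group". The population is the OLE safety set. That is two reporting periods, each applied to both groups.

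The SAP does something else. In Section 17, Table 15, the Placebo/M2951 row holds data from the OLE and what follows it. The M2951/M2951 row holds "Data from both periods (12-Week treatment and OLE period), ie all data collected throughout the study". Section 17.1, Table 16 splits treatment-emergent events in the same way. For switchers, "Only AEs from OLE period will be considered"; for continuers, events count from the first double-blind dose.

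The outputs built on these windows are mostly crude. SAP Section 17.1.1 tabulates the number and percentage of subjects with an event. For hematology and biochemistry, Section 17.3 plans this: "A shift table of baseline versus post-baseline based on the worst NCI-CTCAE grade will be presented by treatment group". Section 17.1.1 also plans exposure-adjusted incidence rates for TEAEs by SOC and PT. Twelve-week safety by group appears only at the primary analysis, on the full Safety Analysis Set (SAF).

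SAP Section 9 declares several other OLE changes (the PD set, ACR20 as an OLE endpoint, the OLE mITT definition). Its readable text does not mention this one.

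**The concern.** The two columns start at different points. Continuers have an extra 12 weeks in which an event can be counted and a laboratory value can be at its worst. If the true event rate were identical in the two groups, the M2951/M2951 column would still show higher crude percentages for any event that leaves the subject able to enter the extension.

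Protocol Section 5.2 says the extension is meant, in part, to collect longer-term safety data. A reader looking for a cumulative effect of M2951 will naturally compare continuers with switchers, and this layout can imitate such an effect. At the final analysis no planned table puts both groups over the same window.

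**Working it through.** **Inputs from the documents.** Protocol Section 5.1 gives screening 4 weeks, double-blind treatment 12, OLE 26 and safety follow-up 4. Protocol Table 1, footnote g, schedules hematology and chemistry at screening, Visits 2 to 8, every OLE visit and the follow-up visit. SAP Table 2 gives the baselines.

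**Assumed inputs.** The documents give no event rates, so the 12-week AE risk r and the per-draw laboratory probability q are shown as ranges. About 28 subjects per column is also an assumption.

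**1. Reproduce the plan's durations.** 4 + 12 + 26 + 4 = 46 weeks with the OLE and 4 + 12 + 4 = 20 without, as stated.

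**2. Windows counted.** Treatment time is 26 weeks for switchers and 12 + 26 = 38 for continuers. The upper limits in SAP Table 4 agree: day 186 / 7 = 26.6 weeks and day 270 / 7 = 38.6 weeks. Both rows also take in follow-up, so observation is 26 + 4 = 30 and 38 + 4 = 42 weeks, a ratio of 1.40.

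**3. Crude AE incidence under equal constant hazards.** Incidence over t weeks is 1 − (1 − r)^(t/12), with t = 30 (a) and t = 42 (b). The standard error of the difference is √[a(1−a)/28 + b(1−b)/28].

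| Assumed 12-week risk | Switchers, 30 wk | Continuers, 42 wk | Gap (points) | Standard error (points) | Gap / SE |
|---|---|---|---|---|---|
| 5% | 12.0% | 16.4% | 4.4 | 9.3 | 0.47 |
| 10% | 23.2% | 30.8% | 7.7 | 11.8 | 0.65 |
| 20% | 42.8% | 54.2% | 11.4 | 13.3 | 0.86 |
| 30% | 59.0% | 71.3% | 12.3 | 12.6 | 0.97 |

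Gaps are taken before rounding. With both columns over the same window, the gap in this model is zero.

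**4. Worst laboratory grade.** Scheduled post-baseline draws are Visits 9 to 12 plus follow-up = 5 for switchers, and Visits 3 to 12 plus follow-up = 11 for continuers. If draws are treated as independent, the chance of at least one abnormal draw is 1 − (1 − q)^k:

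- q = 1%: 4.9% against 10.5%
- q = 2%: 9.6% against 19.9%
- q = 5%: 22.6% against 43.1%

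Draws within a subject are correlated, so these figures show direction rather than predict size.

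**5. Rows where this does not apply.** Protocol Section 5.2 offers the extension to subjects who complete the 12 weeks, and the OLE safety set requires an OLE dose. Events in the first 12 weeks that led to withdrawal or death therefore do not reach the continuers' column. The same holds for laboratory grades for which Protocol Section 6.5.4 requires permanent withdrawal. The calculations in steps 3 and 4 must not be used for those rows.

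**6. Baselines.** Under SAP Table 2, switchers' baseline resets to the last value before the OLE, while continuers keep their pre-treatment baseline. Equalizing the window alone would still leave the laboratory shifts on different baselines.

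**The case against.** The SAP layout has a coherent reading: each column shows what happened since the first M2951 dose. An entire-study column would mix placebo-period events into the switchers' results. The periods are stated in Tables 15 and 16, no between-column test is planned, and Protocol Section 8.6 says that only some safety data will be summarized at the end. Exposure-adjusted TEAE rates are planned in both documents, and exposure time is reported over the same column-specific windows. The randomized 12-week comparison over a common window is already made at the primary analysis, on a better set than the OLE subset. The illustrated gaps rest on assumed rates and stay below one standard error with 28 per column.

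Most of this stands as context. It does not remove the problem. The exposure-adjusted rates are specified by SOC and PT only, so the overview rows (any, related, serious, grade 3 or higher) and the worst-grade laboratory table have no correction. A shift of 0.5 to 1.0 standard errors in a fixed direction matters when safety is read descriptively.

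A common window from the first OLE dose is not neutral either. It sets switchers' first weeks on M2951 beside continuers' time after week 12, so that limit has to be printed with the table.

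A reader might infer more than the documents support:

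- **That every row is inflated, including withdrawal and death.** Entry to the OLE set rules this out.
- **That no common-window comparison exists anywhere.** This is true only of the final analysis.
- **That the change was left undeclared.** Section 9 contains a redacted item, so this can be said only of the readable text.

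**Conclusion.** The point holds within limits. The SAP replaces the protocol's two by-group reports with columns of about 30 and 42 weeks (26 and 38 on treatment). Under equal constant hazards, this alone raises crude incidence in the M2951/M2951 column by about 4.4 to 12.3 points for assumed 12-week risks of 5% to 30%. That applies to adverse events that do not prevent OLE entry. The worst-grade laboratory shift sets the worst of 11 scheduled draws against the worst of 5, apart from grades that require permanent withdrawal.

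The windows and draw counts follow from the documents. The event rates, the constant hazard and the independence of draws are assumptions. The conclusion concerns what the tables can show, and says nothing about whether M2951 has cumulative toxicity.

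**What to change.** In SAP Section 17 and Tables 15 and 16, for the final analysis:

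- Add one AE overview (any, related, serious, grade 3 or higher, leading to withdrawal) with both groups counted from the first OLE dose to the end of study.
- Add one worst-grade laboratory shift table over the same window, with the last pre-OLE value as baseline in both groups.
- Footnote both tables: continuers have already had 12 weeks on M2951, so early-onset events appear only in switchers, and continuers' laboratory baseline is an on-treatment value.
- Extend the exposure-adjusted rates to the overview rows.
- Keep the results counted from first M2951 dose as a separate table with the period in its title.
- Restore the protocol's 12-week and entire-study reports by group on the OLE set, or declare their removal in Section 9.

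All of this uses data already collected. The cost is SAP wording and a few more tables.
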